At Jigme Dorji Wangchuck National Referral Hospital (JDWNRH), Thimphu Bhutan the prevalence of preterm birth was 6.4% (64 per 1000 live birth)(42). This study will be conducted at JDWNRH which is a tertiary care hospital with NICU facility. The participants for the study will be low risk preterm infants since these group of infants are followed up periodically to monitor for developmental outcome, the follow up starts only when the child attends 3 months of corrected age and they miss out on the critical period to start intervention. In Bhutan, due to a shortage of pediatric physical therapists (PT), this group of infants does not receive proper attention and if the parents are taught how to provide a home programme, it helps in empowering the parents and reducing the burden and stress of bringing the child for therapy at the clinic regularly. This will also help the limited number of PTs in the country to provide better care and support to the high-risk preterm infants.

Most of the early intervention programs are resource intensive and requires a multi-disciplinary team. In a setting where there is limited human resources, customized physical therapy intervention will empower parents to provide intervention to their infant within the natural environment of their home with no extra resources required. Involving parents as primary practitioners will help them to understand and respond more knowledgeably to their infant's behaviour, which can promote optimal development. Therefore, the long-term outcome of this study is to provide appropriate physical therapy intervention to infants born preterm post discharge from the neonatal unit so that it can improve the motor development and prevent the neurodevelopmental impairments. The findings from this study will help in providing appropriate physical therapy intervention which involves parent, therapist and infant interactions to enhance the motor development of infants born preterm.

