1.4.3 Inclusion criteria

- Infants who are born <37 weeks' gestation
- Medically stable and off ventilator on discharge from NICU
- Parents who consent to come for follow up.

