1.4.5 Sample size

Sample size calculation will be based on the study by Dusing et al(43). According to the study they found a significant difference in motor performance of infants born preterm who received physical therapist delivered intervention compared to the usual care group. The effect size from the study was Cohen's d of 1.29 for TIMP z- score. Using this data, the total sample size of 22 was obtained using G power program version 3.1. However, with 20% drop out rate a total of 28 infants born preterm would be required with 14 in each group.

[figure not shown]

Figure 2: G power

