1.4.7 Data Collection

The study will be conducted after seeking ethical approval from Institutional Review Board (IRB), Khesar Gyalpo University of Medical Sciences of Bhutan (KGUMBS). The data will be collected at pediatric physiotherapy unit, JDWNRH. Preterm infants referred for high risk follow up clinic at Pediatric Physiotherapy Unit that evaluates neurodevelopmental outcome will be recruited. Oral and written information will be given to parents of the preterm babies fulfilling the inclusion criteria. Parents will be informed regarding the objectives, procedures, risk and benefits of the study. Informed consent will be taken from the parents prior to the study by the principal investigator. Strategies to achieve adequate participant enrolment to reach target sample size will be, establish a link between

the research team and mother and father of each of the subjects included, regardless of the group allocated since randomization.

Randomization will be performed by blindly drawing the slip from the container which will have equal numbers of same size and shape slips and will be performed by the research assistant who will not be responsible for any intervention nor outcome assessment. After randomization the infants in the control group will receive standard care and the infants in the intervention group will receive modified SPEEDI. The principal researcher will provide the modified SPEEDI. The research assistants shall be physical therapist or physical therapy assistants and occupational therapist who has over 2 years of experience in working with pediatric population and will be blinded to the group allocation since they will assess the outcome. These research assistants will be trained to use the measurement tools by the principal researcher. As the study participants are preterm infants, caution will be taken to avoid thermal stress to these infants by keeping the data collection room in pediatric physiotherapy unit warm. During the study process if there are amendments to the study protocol, the information shall be communicated with the IRB and the co-investigators of the study.

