1.4.8 Measurement

Prior to the assessment of motor performance and neurodevelopment, demographic details such as gestational age, length of stay in the hospital and medical diagnosis will be recorded. The measurement will be taken at 40 weeks of post menstrual age, 1 month, 2 months and 3 months of corrected age by the research assistants who will be blinded to group assignment.

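### Gestational age is in neither the draw nor the planned ANOVA; with 14 infants per arm, prespecify it as a covariate so that chance imbalance cannot tip or mask a modest effect

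*Combined protocol and SAP*

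**What the plan says.** Allocation (section 1.4.7) is a single draw: "Randomization will be performed by blindly drawing the slip from the container which will have equal numbers of same size and shape slips". No strata, blocks or minimisation are described anywhere.

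Eligibility (section 1.4.3) is "Infants who are born <37 weeks", with no lower limit. The Introduction narrows this in words: "The participants for the study will be low risk preterm infants". Section 1.4.4 excludes haemorrhage of grade 3 and above, hypoxic ischemic encephalopathy, hydrocephalus, major surgery and feeding tubes, among others.

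Gestational age is collected. Section 1.4.8 states that "demographic details such as gestational age, length of stay in the hospital and medical diagnosis will be recorded". It has no further role. Section 1.4.6 lists group and time as the only independent variables, and section 1.4.10 plans a two-way mixed ANOVA for motor performance and another for neurodevelopment, naming no covariate.

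The sample size (section 1.4.5) rests on a Cohen's "d of 1.29 for TIMP z- score", from which "the total sample size of 22 was obtained using G power program version 3.1"; it adds that "with 20% drop out rate a total of 28 infants born preterm would be required with 14 in each group".

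**The concern.** A draw with equal numbers of slips fixes the arm totals but balances no prognostic factor. In a trial of 28 infants, one arm can easily receive more of the most immature infants. If gestational age at birth affects how quickly TIMP or RNDA scores rise over the first three corrected months, the between-arm contrast then contains part of that natural course as well as the programme's effect. Gestational age has to be known at entry, because eligibility depends on it, yet the plan uses it neither to prevent an imbalance nor to adjust for one. A reader of the results would see the imbalance in the baseline table and have no prespecified analysis that accounts for it.

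**Working it through.** **1. The plan's own figure.** Inputs from sections 1.4.5 and 1.4.10: d = 1.29, alpha 0.05, 1:1 allocation. Two-sided testing and power 0.80 are assumed, because the text states neither. A two-sample t-test (noncentral t) needs 11 per arm, or 22 in total, with power 0.82. Dropout: 22 / 0.80 = 27.5, rounded up to 28. Both stated figures are reproduced. Power at 14 per arm is 0.91.

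**2. How often imbalance occurs.** Under an unstratified 1:1 draw, the standardised difference in mean gestational age has SD √(2/n).

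| Infants per arm | SD of the difference | 95% limit | Chance of 0.5 or more, either direction |
|---|---|---|---|
| 14 | √(2/14) = 0.378 | ±0.74 | 18.6% |
| 11 (completers) | √(2/11) = 0.426 | ±0.84 | 24.1% |

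**3. Size of the shift, counting very preterm infants.** The documents give neither a gestational-age distribution nor a link between gestational age and TIMP, so both are assumed. Take K infants of the 28 born before 32 weeks, split 14/14 (drawing without replacement is inferred from the equal numbers of slips). The hypergeometric chance that the arms differ by at least 4 such infants is:

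- K = 6: 0.165
- K = 8: 0.209
- K = 10: 0.236

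If these infants score 0.5 to 1.0 SD lower, a difference of 4 shifts the contrast by 0.5 × 4/14 = 0.14 SD to 1.0 × 4/14 = 0.29 SD. Against 1.29, that is 11% to 22%.

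**4. The same question with gestational age continuous.** Shift = correlation with TIMP × standardised imbalance. For example, 0.3 × 0.5 = 0.15 SD and 0.5 × 0.74 = 0.37 SD. At a high assumed correlation of 0.7, 0.7 × 0.74 = 0.52 SD.

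**5. Comparison with the significance threshold.** At 14 per arm, the smallest significant difference is 2.056 × √(2/14) = 0.78 SD. All the shifts above are smaller.

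**6. Consequence in an unlucky draw.** This was simulated with a t-test at one time point as a stand-in for the group comparison, at an imbalance of 0.74 (the 95% limit) and 14 per arm.

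| Assumed correlation | False-positive risk favouring SPEEDI (nominal 2.5%), imbalance in its favour | Power for d = 1.29, imbalance against it (0.91 when balanced) |
|---|---|---|
| 0.3 | 7% | 0.78 |
| 0.5 | 12% | 0.67 |
| 0.7 | 19% | 0.50 |

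For an illustrative smaller effect of d = 0.8 with the imbalance against SPEEDI, power at correlations 0.3 and 0.5 is 0.31 and 0.16 unadjusted, and 0.51 and 0.58 adjusted.

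**7. Effect of adjustment.** With gestational age as a covariate, the conditional two-sided type I error in the same simulations is about 5%. Adjusted power for d = 1.29 at 11 per arm is 0.82, 0.85 and 0.91 for correlations of 0, 0.3 and 0.5, so 22 (28 with dropout) still suffices.

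**The case against.** Four counter-arguments carry weight.

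- **The shift is modest.** A reader might infer that an imbalance could pass for the programme's whole effect. The figures do not support that: 0.14 to 0.29 SD is far below both 1.29 and the 0.78 SD needed for significance. The chances in steps 2 and 3 also cover both directions, so those for an imbalance favouring one named arm are half as large. This stands.
- **The plan already removes part of the problem.** A reader might infer that nothing in it does. In fact all infants are tested at 40 weeks postmenstrual age and then at 1, 2 and 3 months corrected age, which removes age-at-test differences. Baseline is also a level of time in the ANOVA, so a group-by-time test removes a stable baseline gap. A difference in rate of change linked to gestational age remains, and section 1.4.10 does not say which ANOVA term is the test.
- **The sample may be narrower than the entry criterion.** The low-risk description and the exclusions may leave few very preterm infants. A difference of at least 4 has probability 0.10 with four such infants, 0.04 with five, and is impossible with three or fewer. This lowers the likely shift but does not remove the point. With five, a difference of at least 3 still has probability 0.33, and with three it has 0.22; a difference of 3 shifts the contrast by 0.11 to 0.21 SD (3/14 × 0.5 to 1.0). No eligibility criterion enforces low risk by gestation.
- **Stratifying the draw has a cost.** The principal researcher delivers the intervention and so learns each allocation. With small fixed sets of slips, the last slip in a set could often be guessed. This stands, and it favours adjustment in the model over a change to the draw.

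**Conclusion.** The point holds as an improvement to the analysis. Chance imbalance in gestational age is common at this size (about 19% of draws reach 0.5 standardised units), and the planned model cannot account for any resulting difference in rate of change. Under the stated assumptions the contrast moves by about 0.14 to 0.29 SD, less if few infants are very preterm; the continuous calculation reaches 0.37 to 0.52 SD only with a draw at the 95% limit and correlations of 0.5 to 0.7. Such shifts can tip a borderline result or hide an effect smaller than planned.

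A reader might also infer that the randomisation is invalid or the test's error rate wrong. Neither follows: averaged over all draws the unadjusted test keeps its 5% type I error. What is at stake is bias conditional on the draw obtained, and lost precision. The size rests on assumed correlations, score gaps and numbers of very preterm infants, none of which the documents give.

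**What to change.** In section 1.4.10, prespecify gestational age at birth, continuous in weeks, as a covariate in the TIMP and RNDA mixed models, including its interaction with time. State that the adjusted group-by-time effect is the main result. Settle this before outcome data are examined.

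**Cost:** no extra infants and no new data. With four assessment times, a linear term uses 1 between-subject degree of freedom (26 to 25 with 28 infants), and its interaction with time uses 3 within-subject degrees of freedom (26 × 3 = 78 to 25 × 3 = 75). The model assumes a roughly linear relation with weeks of gestation.

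**Optional:** stratify the draw by gestational age. In simulation with two strata and blocks of 4 (assumed cut-points and distributions), the chance of a standardised imbalance of 0.5 or more fell from about 19% to 2–4%. If stratification is used, avoid small fixed sets of slips because of the predictability described above. It is not needed for the covariate to do its work.

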1.4.8 Measurement

Prior to the assessment of motor performance and neurodevelopment, demographic details such as gestational age, length of stay in the hospital and medical diagnosis will be recorded. The measurement will be taken at 40 weeks of post menstrual age, 1 month, 2 months and 3 months of corrected age by the research assistants who will be blinded to group assignment.

1.4.8.1 Motor performance

Motor performance will be assessed using The Test of Infant Motor Performance (TIMP) version 5.1, administered when the child is awake (Brazelton state 3,4 or 5). The infant should wear minimal clothing as possible. Testing will be performed on a firm surface with no distractions. No more than 3 trials will be allowed for each elicited item. If the infant gets fussy and irritable during the process of assessment, breaks can be taken in between the assessment and if the parents are not comfortable with the procedure the parents will have every right to withdraw and discontinue their infant's participation from the study. However, if the parent consents to continue the assessment, items that remain during the first session shall be

completed in second session within 24 hours so that it assessor does not have to redo the whole assessment again.

The Test of Infant Motor Performance (TIMP) was developed to assess functional motor performance in infants from 34 weeks postmenstrual age (PMA) through 4 months corrected age. The TIMP is a 42- item assessment with 13 dichotomous items scored based on observation of spontaneous movement and 29 elicited items with 4 to 7-point rating scales based on handling of the infant in a variety of positions in space. The test takes 20-35 min to administer and score with variation based on age and tolerance of the infant and the experience of the tester. It has been described as one of the best tools to discriminate between age-appropriate and delayed motor performance in preterm and term infants, and to predict later motor development. The TIMP is a valid and reliable tool developed to detect typical and atypical performance in preterm infants and evaluate the effect of an intervention on the infant motor performance(44-46). The assessment tool has been also used in multiple clinical trials to evaluate the effectiveness of therapy intervention.

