1.4.10 Statistical Analysis

Statistical analysis will be performed using Statistical Package for Social Sciences (IBM SPSS statistics for windows, version 28). Shapiro Wilk test will be used to test for normality of data. Descriptive statistics will be used to analyze patient's demographic data. To investigate the effect of physical therapist intervention on motor performance two-way mixed ANOVA will be performed. To investigate the effect of physical therapy intervention on neurodevelopment two-way mixed ANOVA will be performed. The level of significance will be set at a p-value < 0.05.

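### Section 1.4.8.1 describes no way to stop or skip one TIMP assessment and stay in follow-up, so some infants who tolerate testing poorly may be lost from later visits, including 3 months

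*Combined protocol and SAP*

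**What the plan says.** Section 1.4.8.1 deals with an infant who becomes irritable during the TIMP. The first response is a break. For a parent who is uneasy, the text then says "if the parents are not comfortable with the procedure the parents will have every right to withdraw and discontinue", and what is discontinued is the infant's participation in the study, not that day's test. The other branch reads "However, if the parent consents to continue the assessment, items that remain during the first session shall be" completed at a second session within 24 hours. No other readable section describes declining a single assessment and returning for the next.

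Section 1.4.8 sets the timetable: "The measurement will be taken at 40 weeks of post menstrual age, 1 month, 2 months and 3 months of corrected age". The objective in 1.3 is the comparison at 3 months.

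Section 1.4.5 treats dropout as a number only: "However, with 20% drop out rate a total of 28 infants born preterm would be required with 14 in each group". Section 1.4.10 plans a two-way mixed ANOVA in SPSS for motor performance and for neurodevelopment. It gives no missing-data rule and no analysis set.

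**The concern.** Discomfort with one research test and the wish to leave a trial are different decisions. The text offers only leaving the study or completing the test, so a parent who would have missed one visit and come back may be recorded as withdrawn. Visits still to come are then lost, although the standard schedule already provides for them.

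This loss would arise while the outcome itself is being measured. If infants who tolerate handling poorly also tend to score differently, those who remain are a selected group. The sample-size allowance replaces numbers; it does not correct selection. An analysis can use the visits that were made, but it cannot recover a 3-month score that was never taken.

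**Working it through.** **Inputs.** Effect size: "d of 1.29 for TIMP z- score" (1.4.5). Size before dropout: "the total sample size of 22 was obtained using G power program version 3.1". Allowance: 20%, giving 28, or 14 per arm (1.4.5). Significance: "The level of significance will be set at a p-value < 0.05" (1.4.10). Sidedness is not stated and the target power is not in the readable text (the G power figure is not shown), so two-sided 0.05 and 80% are assumptions.

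**Step 1: the plan's own figures.** A two-sample t-test with d = 1.29, two-sided 0.05 and 80% power needs 10.49 per arm, rounded up to 11, or 22 in total. Then 22 / (1 − 0.20) = 27.5, rounded up to 28. Both figures reproduce. The 22 does not identify the power uniquely: one-sided 0.05 with 22 infants gives 89.9%.

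**Step 2: power after loss.** Power comes from the noncentral t distribution with noncentrality d × √(n1·n2/(n1+n2)) and n1+n2−2 degrees of freedom. The number of such withdrawals is not in the documents; 2 or 3 is an assumption.

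| Infants analysed | Lost | Noncentrality | Power |
|---|---|---|---|
| 14 + 14 | 0 | 3.41 | 90.7% |
| 14 + 12 | 2, one arm | 3.28 | 88.2% |
| 14 + 11 | 3, one arm | 3.20 | 86.6% |
| 11 + 11 | 6 (planned) | 3.03 | 82.1% |
| 14 + 8 | 6, one arm | 2.91 | 79.1% |

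Two or three losses leave power above the level the plan accepts at 22 completers. Even six losses all from one arm leave it near 80%. Dropout for other reasons draws on the same six places.

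**Step 3: bias, as an illustration only.** Assume scores are normal with SD 1, the control mean is 0, and infants below the control arm's lower-third cut-off (c = −0.431) withdraw with probability w, by the same rule in both arms. For an arm with mean m, put z = c − m. The retained mean is [m − w(mΦ(z) − φ(z))] / [1 − wΦ(z)], and the loss is wΦ(z).

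- Control (m = 0): Φ = 0.333, φ = 0.364. For w = 0.3 the retained mean is 0.3 × 0.364 / 0.90 = 0.121, with 10% lost. For w = 0.6 it is 0.6 × 0.364 / 0.80 = 0.273, with 20% lost.
- Intervention (m = 1.29): z = −1.721, Φ = 0.0427, φ = 0.0907. The retained means are 1.318 (1.3% lost) and 1.346 (2.6% lost).
- Observed difference: 1.318 − 0.121 = 1.20 for w = 0.3, and 1.346 − 0.273 = 1.07 for w = 0.6, against a true 1.29. A simulation with 14 per arm gives 1.197 and 1.075.
- With no true effect and the same rule in both arms, the expected difference stays at 0.

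The illustration ties withdrawal directly to the analysed score, so it lies towards the strong end. A weaker link gives a smaller shift.

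**Step 4: does retention reach the analysis?** A conventional mixed ANOVA needs all four visits for each infant. If 2 or 3 infants of one arm skip one visit and return, it still analyses 14 + 12 or 14 + 11, as if they had left. A change to 1.4.8.1 alone would leave the analysed sample as it was.

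**The case against.** A reader might infer that infants who test badly will be lost from every later visit. The documents do not support that. Withdrawal is a right and is not automatic; nothing forbids a parent from declining one session and coming back; breaks come first, and the 24-hour second session is itself an accommodation. The trigger is fussiness together with parental discomfort, and no section links either to a low TIMP score.

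A reader might also infer a threat to power, quoting 78% with 20 completers or 73% with 18. Those figures need 8 and 10 losses, more than the six allowed for and far more than the 2 or 3 assumed here. Likewise, an arm mean raised by 0.24 SD requires exactly the two lowest scorers of 14 to leave one arm and none to leave the other. Nothing in the documents suggests this: the TIMP procedure is the same in both arms and the assessors are to be blinded.

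Other points on that side stand. Under a common mechanism the bias is nil without a true effect and, in the illustration, towards zero with one. Only the first three of the four sessions have later visits to lose; stopping the 3-month test loses the endpoint under any wording. The text does not say whether the 40-week test precedes randomisation. Consent pages were removed and the procedure figure is not shown, so the parent information may already cover refusal of one assessment.

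These points limit the size and certainty of the concern. They do not supply the missing option in 1.4.8.1, which is the text that assessors would follow at the session.

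**Conclusion.** The point holds as a gap in trial conduct. Beyond breaks, the stated choices for an uncomfortable parent are withdrawal from the study or completion within 24 hours, and no readable section describes missing one assessment while staying in follow-up. Some infants may therefore be lost needlessly, including from the 3-month comparison. The frequency and any relation to motor score are unknown.

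The 20% allowance covers the power loss from 2 or 3 such withdrawals: about 87 to 88% at d = 1.29, on a two-sided t-test. What remains is avoidable and possibly outcome-related missing data. With a true effect, such loss could shift the estimated difference, by roughly 0.1 to 0.2 SD under the assumed rule in Step 3. That range is an illustration, not an estimate for this trial.

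**What to change.** - **Section 1.4.8.1.** Separate stopping or skipping this assessment from withdrawing from the study. A parent may end that day's test and remain enrolled; the reason is recorded by arm; the infant is invited to all later visits. The 3-month TIMP is sought for every randomised infant unless the parent withdraws consent for further data collection. The right to full withdrawal stays as it is. Add how a TIMP stopped part-way is scored or set to missing, and check that the parent information says the same.
- **Section 1.4.10.** Replace the mixed ANOVA with a likelihood-based linear mixed model for group, visit and their interaction, using all available visits and reporting the 3-month contrast. SPSS provides this. A skipped visit then does not remove the infant. The model assumes that missingness depends only on observed data, so the recorded reasons should be reported by arm.

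The cost is a few sentences in two sections, a check of the parent information, some missing intermediate visits, and slightly more analysis work. The later visits are already scheduled for both arms.
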